## 5.3 Handling of Missing Data and Outliers

### 5.3.1 Safety

No replacement of missing data will be done. All subjects with safety data and all safety data recorded in the eCRFs will be included in the safety analyses. No search for outliers will be performed.

In all subject listings, partial and missing data will be clearly indicated as missing.

#### 5.3.1.1 Immediate

For unsolicited non-serious systemic AEs, a missing response to the “Immediate” field is assumed to have occurred after the 20-minute surveillance period and will not be imputed.

#### 5.3.1.2 Causality

Unsolicited AEs and SAEs with missing causality will be considered as related to vaccination.

#### 5.3.1.3 Measurements

Missing measurements (for temperature or length) will remain missing and will not be imputed. Nevertheless, the following rule will be applied: If the measurement (temperature or length) is missing the value after the decimal point, the data will be analyzed by replacing “MD” with zero. For example, a “102.MD $^{\circ}\text{F}$ ” daily temperature will be considered as “102.0 $^{\circ}\text{F}$ ” during the analysis.

#### 5.3.1.4 Intensity

No replacement of the missing qualifier will be done. For analysis, the missing class for the AE qualifier will be provided in the descriptive tables.

### **5.3.1.5 Start Date and Stop Date**

No replacement of missing dates will be performed.

For instance:

- If the onset of an AE cannot be calculated due to a missing start date, then the onset will be considered as missing
- If the stop date of an unsolicited AE is missing, then the duration of that AE will be considered as missing
- If the stop date of a solicited reaction continuing after the solicited period is missing or incomplete, then the number of days of occurrence of that solicited event will be considered as missing

All missing and partially missing dates will be listed where appropriate.

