In addition to recording solicited reactions, the parent/guardian will be instructed to record any other medical events that may occur from Visit 1 to Visit 2 (Diary Card 1) for all subjects and from Visit 2 to Visit 3 (Diary Card 2) for subjects receiving 2 doses. Space will be provided in the diary card for this purpose. For each unsolicited non-serious AE, the following information is to be recorded:

- Start and stop dates^a
- Intensity of the event:
 - For measurable unsolicited non-serious AEs that are part of the list of solicited reactions, the size of the AE as well as the temperature for fever will be collected and analyzed based on the corresponding scale used for solicited reactions (see [Table 9.1](#) and [Table 9.2](#))
 - Other unsolicited non-serious AEs will be classified according to the following intensity scale:
 - Grade 1: No interference with activity
 - Grade 2: Some interference with activity
 - Grade 3: Significant; prevents daily activity
- Action taken for each AE, if any (e.g., medication)

The action taken by the parent/guardian to treat any **unsolicited AEs** will be classified in the eCRF using the following scale:

0: None

1: Medication (self-medication with an existing prescription or over-the-counter medication)

2: Health care provider contact (no new medication prescribed)

^a The stop date of all related AEs will be actively solicited. For other events, the Investigator will provide the stop date when it becomes available. Adverse events for which no stop date was obtained during the course of the trial will be considered as ongoing at the end of the trial.

3: Health care provider contact and prescription of a new medication (health care provider instructed subject to take a new medication, either an over-the-counter medication or one requiring a written prescription)

- Whether the AE led to discontinuation
- Whether the AE was related to vaccination (for unsolicited systemic AEs)

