#### 4.4.1.1.5 Number of Days of Occurrence

Number of days of occurrence during the period considered will be derived from the daily intensities computed as described in [Section 4.4.1.1.1](#). It corresponds to the number of days with daily intensities of Grade 1, Grade 2, or Grade 3. The number of days of occurrence during the solicited period with a specified intensity may also be derived. For subjects who received 2 doses, the worst case-scenario will be used for the post any dose summary (i.e., the larger number of days will be used if present for both doses, or the available number of days will be used if present for either dose).

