#### 4.4.1.1.6 Overall Number of Days of Occurrence

If a reaction is ongoing at the end of the solicited period, then the overall number of days of occurrence will be derived from the daily intensities and the stop date of the reaction after the end of the solicited period. The overall number of days of occurrence will be:

$$(\text{stop date} - \text{last vaccination date}) + (\text{number of days of occurrence within the solicited period}) - \text{length of the solicited period} + 1$$

If the stop date is missing or incomplete (contains MD), the overall number of days of occurrence will be considered as Missing. For subjects who received 2 doses, the worst-case scenario will be used for the post-any dose summary (i.e., the larger number of days will be used if present for both doses, or the available number of days will be used if present for either dose).

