##### 4.4.1.2.4 Duration

Duration will be derived from the start and stop dates of the unsolicited non-serious AE provided in the clinical database:

stop date of unsolicited non-serious AE - start date of unsolicited non-serious AE + 1.

The duration will be considered as missing only if 1 or both of the start and stop dates of the unsolicited non-serious AE is missing or partially missing. For subjects who received 2 doses, the worst-case scenario will be used for the post-any dose summary (i.e., the longer duration will be used if present for both doses or the available duration will be used if present for either dose).

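### SAP 5.3.1.5 conflicts with 4.4.1.1.5 and 4.4.1.1.6 on days of occurrence, and events with no stop date lose a known minimum duration

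*SAP*

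**What the plan says.** Four SAP rules and one protocol footnote bear on this point.

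- **SAP 4.4.1.1.5** defines the number of days of occurrence from the daily intensities: "It corresponds to the number of days with daily intensities of Grade 1, Grade 2, or Grade 3". No stop date enters. This is the duration measure named in the solicited safety endpoints (SAP 4.3.1.2, items 2 and 3, Day 0 to Day 7) and in the planned presentation of solicited reactions (SAP 5.1.3.1).
- **SAP 4.4.1.1.6** defines a second quantity, the overall number of days, for reactions that run past the diary: "If the stop date is missing or incomplete (contains MD), the overall number of days of occurrence will be considered as Missing". For children with two doses, the post-any-dose summary takes the larger value if both exist, "or the available number of days will be used if present for either dose".
- **SAP 5.3.1.5** covers the same situation without the word *overall*: "If the stop date of a solicited reaction continuing after the solicited period is missing or incomplete, then the number of days of occurrence", with the conclusion that this number is missing. For unsolicited AEs it says "If the stop date of an unsolicited AE is missing, then the duration of that AE will be considered as missing".
- **SAP 4.4.1.2.4** agrees for unsolicited AEs ("The duration will be considered as missing only if 1 or both of the start and stop dates" is missing or partial) and has a matching two-dose rule.
- **Protocol 9.3.1.3.3**, in a footnote on unsolicited non-serious AEs, gives such events a status when the trial closes: "Adverse events for which no stop date was obtained during the course of the trial will be considered as ongoing".

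**The concern.** There are two separate problems.

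First, 5.3.1.5 and 4.4.1.1.5 give different answers for the same child. One keeps a count fully observed in the diary. The other deletes it because a later date is absent. Two programmers could each follow the SAP and produce different tables for a stated safety endpoint.

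Second, an event with a known start that is still running at last contact has a censored duration, not an unknown one. Setting it to missing drops the information that it lasted at least so many days. Events still running when observation ends tend to be longer than those that have resolved, so summaries of the remainder should come out short. The two-dose rule is described as worst case, yet it can do the reverse when the longer of the two values is the one set to missing.

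At stake are descriptive duration summaries for a higher dose that the sponsor intends to add to the labeling for this age group (Protocol 1.4).

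**Working it through.** The plan gives no figure on this point, so there is none to reproduce. The steps below apply the SAP's own formulas to simple cases.

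**1. The conflict.** Take a solicited reaction graded at least 1 on every diary day, continuing afterwards, with no stop date.

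| Rule | Quantity | Result |
|---|---|---|
| SAP 4.4.1.1.5 | days of occurrence, Day 0-7 | 8 |
| SAP 4.4.1.1.6 | overall number of days | missing |
| SAP 5.3.1.5, literal | days of occurrence | missing |

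The trigger in 5.3.1.5 is the same as in 4.4.1.1.6. The quantity it names is the one in 4.4.1.1.5.

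**2. Known minimum, solicited reaction.** SAP 4.4.1.1.7 calls a reaction ongoing only if it is at least Grade 1 on the last diary day and again in the ongoing period. The earliest possible last day is therefore Day 8. The formula in 4.4.1.1.6 is (stop - vaccination) + days in period - length of period + 1, with length 8 for Day 0 to Day 7.
- Present Day 0-7 and ongoing: 8 + 8 - 8 + 1 = 9, so at least 9 days.
- Onset on Day 7 and ongoing: 8 + 1 - 8 + 1 = 2, so at least 2 days.

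The SAP records both overall values as missing. (The formula needs length 8. With 7, the first case would give 10, one day too many.)

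**3. Known minimum, unsolicited AE.** Duration is stop - start + 1 (4.4.1.2.4). Take a one-dose child with an AE that starts on Day 8 and is still running at Visit 2 (Day 28 to 35). The minimum is 28 - 8 + 1 = 21 to 35 - 8 + 1 = 28 days. The SAP records it as missing.

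**4. Two-dose rule.** Dose 1: at least 9 days, no stop date, so missing. Dose 2: 1 day. The post-any-dose overall value is 1, the only one available. The known minimum is max(9, 1) = 9.

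**5. Possible size.** The documents give no share of reactions ongoing after Day 7 (q), no share of these without a stop date (m), and no mean durations. The following are assumptions for illustration: mean 2 days if resolved, 12 days if ongoing, and a known minimum of 9 days.
- True mean = (1 - q) x 2 + q x 12
- SAP mean = [(1 - q) x 2 + q(1 - m) x 12] / (1 - qm)
- Mean using the minimum = (1 - q) x 2 + q(1 - m) x 12 + qm x 9

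For q = 5% the true mean is 1.90 + 0.60 = 2.50.

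| m | SAP mean | shortfall | mean using the minimum |
|---|---|---|---|
| 10% | 2.44/0.995 = 2.45 | 2% | 2.485 |
| 30% | 2.32/0.985 = 2.36 | 6% | 2.455 |
| 50% | 2.20/0.975 = 2.26 | 10% | 2.425 |
| 100% | 1.90/0.95 = 2.00 | 20% | 2.350 |

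Over the same range of m, q = 2% gives 2.18 to 2.00 (true 2.20) and q = 10% gives 2.91 to 2.00 (true 3.00). These figures concern the overall number of days. Values of 9 or 12 cannot occur in the Day 0-7 count, whose maximum is 8.

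**The case against.** The strongest reply is that 5.3.1.5 has simply lost the word *overall*. It shares its trigger with 4.4.1.1.6, and on that reading the displayed Day 0-7 count is never touched. This is the likeliest intent. It does not remove the conflict, because the text as written names the other quantity.

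The protocol also works to obtain stop dates. They are actively sought for all related AEs (footnote in 9.3.1.3.3). By convention, all injection site AEs and all solicited systemic reactions count as related (9.3.1.3.6). Likely related events that persist at the end of the trial are followed, and the sponsor is told when they disappear. The SAP derives ongoing status and lists missing dates. All this stands, and it suggests that few solicited reactions will be affected. It is not complete cover. For unrelated events the stop date comes only if it becomes available, follow-up may end once a condition is stable or chronic (Protocol 5.1.4), and children lost to follow-up are not pursued for further safety data (5.2.11).

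The footnote that treats undated events as ongoing belongs to unsolicited AEs. For solicited reactions, the known minimum rests on SAP 4.4.1.1.7 instead. How duration will be displayed also depends on table shells kept in a separate file (SAP section 6). SAP Table 5.1 lists means and quartiles for continuous safety data, but SAP 5.1.3.1 does not name duration among the analyses of unsolicited AEs.

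A reader might infer that the plan strips the longest reactions out of the duration endpoints. The documents do not support that. Long events with a stop date are kept, and short late-onset events can lack one too, as the Day 7 case shows.

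**Conclusion.** The point holds as a minor one, in two parts. SAP 5.3.1.5 contradicts 4.4.1.1.5 and 4.4.1.1.6 and must be reconciled with them. Independently of that, overall days and unsolicited AE duration are set to missing where a minimum is known, and the two-dose rule can then report a value below that minimum.

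Any bias in these summaries should be downward, provided the events without a stop date are on average longer than those with one. Its size cannot be found from the documents. Under the assumed inputs with 5% ongoing, it is 2% to 6% when 10% to 30% of ongoing reactions lack a stop date. It reaches 20% only if all of them do.

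It would go too far to conclude that the comparison of doses is distorted. Nothing in the documents shows that stop dates will be missing more often in one group, and these summaries are descriptive and untested. Fever non-inferiority, occurrence, intensity and immunogenicity use none of these rules.

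**What to change.** 1. **SAP 5.3.1.5:** state that only the *overall* number of days is missing when the stop date is missing or incomplete, and that the Day 0-7 count is always computed from the daily grades under 4.4.1.1.5.
2. **SAP 4.4.1.1.6, 4.4.1.2.4 and 5.3.1.5:** for an event with a known start and no stop date, report by group the number ongoing, with the minimum duration to last contact shown as >= x days, or use a censored summary. Do not place these events automatically in the longest duration class, because a Day 7 onset may have only 2 known days. No date is imputed, so the rule against replacing missing dates is respected.
3. **Post-any-dose rules in 4.4.1.1.6 and 4.4.1.2.4:** do not let a shorter value from the other dose stand in for a missing value whose known minimum is longer.

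The cost is SAP wording and minor programming. Reported durations become slightly longer.

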### **5.3.2 Immunogenicity**

Missing data will not be imputed. No test or search for outliers will be performed.

## **5.4 Interim/Preliminary Analysis**

No planned interim/preliminary analyses are planned.

## **5.5 Determination of Sample Size and Power Calculation**

[REDACTED]

## 5.6 Data Review for Statistical Purposes

A review of the data is anticipated through the data review process led by CDM before database lock.

## 5.7 Changes in the Conduct of the Trial or Planned Analyses

Not applicable.

## 6 Statistical Analysis Plan TLF Shells

The second part of the SAP (in a separate file) describes the tables, listings, and figures that are planned to be included in the CSR, as well as other outputs for internal purpose only.

This document (SAP core body part), and formal review/approval includes also the following document:

SAP - TLF part (at the time of review/approval)	
CLI number:	CLI_1684182
Version and date:	Version 1.0 – 2017

